Sample size calculations were performed using GLIMMMPSE Version 3.⁴³ Though a Bayesian model averaging approach will be used, sample size calculations using a non-Bayesian approach are applicable here because they correspond to the model that is believed to be most likely true *a priori*, and also because we plan to use uninformative priors on the parameters in the model, which makes our analyses comparable to the non-Bayesian approach that is used for sample size calculations. As we do not have pilot data to inform our sample size calculations for the NAS/non-NAS group, our sample size calculations are based on the group means by gender that were observed in the pilot study on “total puffs” and a standard deviation of 5.5.³¹ Given NAS smokers’ preexisting misperceptions about natural/organic cigarettes, we anticipate that group means will be more extreme in the NAS/non-NAS group.⁴⁴ Thus, the minimum sample size required for Aim 3 analyses should be sufficient to address the Aim 2 analyses. Assuming an intraclass correlation between repeated measurements of 0.5, 40 total subjects are needed to detect a significant interaction between gender and condition (natural/organic vs conventional/own brand) at 90% power and a significance level of 5%, while 99% power requires 68 subjects. Since these assumptions use information based on only 22 subjects in the pilot study, sample size calculations were also performed with an effect size 50% smaller and a

covariance matrix 50% larger than assumed: under these conditions, 90% power is achieved with 228 total subjects. Fewer subjects are needed to detect differences hypothesized in Aim 1 at each given power; for example, under the smallest effect size observed in the topography pilot data (which assumes a mean difference of 120ml with standard deviation 165ml), 120 subjects are needed to achieve 90% power under an effect size that is 50% smaller and covariance matrix that is 50% larger than assumed. Thus, we will enroll 125 participants per cigarette type (250 total, though we have budgeted for up to 300 participants to account for loss to follow up) to ensure at least 228 participants complete the full study. Our proposed sample size is adequate to detect a similar topography effect size to our pilot study, examine moderation by NAS preference and gender, and allow for adjustments to the significance level due to multiple comparisons.

Statistical analyses

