We will consider models that: 1) allow the effect of the condition (conventional, organic, and natural) to differ based on NAS-smoking status and gender (as hypothesized); 2) allow the effect of the condition to differ based only on NAS-smoking status; 3) allow the effect of the condition to differ based only on gender; and 4) do not allow the effect of the condition to differ based on NAS-smoking status or gender. We will also consider models that combine the effects of the natural and organic conditions, as we believe the effects of these two conditions could be similar for our outcomes. We will also consider in the model an effect for the own brand

condition (which may or not depend on NAS-smoking status and gender), period effects, random effects, and effects for other covariates that may be predictive of the outcome. Bayes factors will be used to determine if the effect of the condition depends on NAS-smoking status or gender, and if a combined effect (one effect vs two) should be used in the model for the natural and organic conditions.

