Baseline covariates that may be significant predictors of the outcome will be considered in the model because including predictors that reduce noise may increase the efficiency of the analyses in H(1.1) – H(3.4). We will use Bayesian model averaging to control for other covariates and estimate the parameters in each considered model.⁴⁹ Bayesian model averaging incorporates model uncertainty into inference and has several other advantages over the approach that relies on choosing a single best model among many candidate models.⁵⁰ In general, Bayesian model averaging uses all possible models that can be considered given a set of covariates (there are 2^k possible models when there are k covariates) and estimates parameters by using a weighted average of the estimates obtained from each model, where better fitting models are given larger weights (see Raftery et al. (1997)⁴⁹ and Hinne et al. (2020)⁵⁰ for more details). The following baseline measures in particular will be considered (which are *a priori* expected to be related to the outcomes that are used to test hypotheses H(1.1) – H(3.4)): score on the organic products scale, age, education, heaviness of smoking, perceived health, and own brand total puff volume (for all outcomes except the topography outcome, which uses total puff volume as the response); however, other covariates collected at baseline (e.g. race, ethnicity) will also be considered in the model. Using Bayes factors to first choose the best representation for the effects of the condition in the model and using Bayesian model averaging to estimate the parameters in the model will be repeated separately for each outcome, so that we have one model for each of the four outcomes: expectancies, subjective ratings, topography, and biomarkers of exposure.

A continuous response is a reasonable assumption for all outcomes except those in H(1.1), H(2.1), H(3.1), and H(4.1); in these hypotheses, the outcome will be modeled as a binary response (0/1) and an alternative model formulation (e.g. logistic mixed model) consisting of the same model parameters (e.g. same linear predictor as the other outcomes but using a logit link function) will instead be used to model the probability that the outcome is equal to 1. Other outcomes may also be modeled as a binary response depending on their distribution (more details are provided below).

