Preliminary analyses assume there are no carryover effects. However, sensitivity to this assumption will be examined by considering models that instead assume there are carryover effects (as described above); if there are carryover effects, then the effect of the condition also depends on the period (in addition to possibly gender and NAS-smoking status). For the main analyses that assume there are no carryover effects, we will use uninformative priors for all model parameters. Markov Chain Monte Carlo (MCMC) sampling will be used to estimate the posterior distribution of the model parameters; if there is a convergence issue for a parameter (e.g. if variance hyperparameters are on the boundary) or if model fit is a concern, we will instead consider weakly informative priors.⁵¹ When uninformative priors are used, results using a single candidate model with a Bayesian model averaging approach are equivalent to non-Bayesian, frequentist analyses (i.e. maximum likelihood estimation techniques).

To assess sensitivity of our choice of prior for the carryover effect, we will use a process similar to Grieve (1985).⁴⁸ To allow for a carryover effect, we will first use a Normal distribution with mean 0 and variance σ_{co}^2 as the prior for the carryover effects, and use an uninformative prior for σ_{co}^2 that ranges between 0 and ∞ . Next, we will let π be the prior odds of M_0 to M_1 , where M_0 is the model above without carryover effect and M_1 is the model with carryover

effect. We can then assess the impact of a range of prior belief in a carryover effect by repeating analyses for different values of π . The primary analyses assume there is no carryover effect, which corresponds to π equal to 1, while sensitivity analyses will assume there is a carryover effect, which corresponds to $0 \leq \pi < 1$.

Since MCMC methods will be used, the entire posterior distribution corresponding to the parameters of interest will be estimated and can be produced as figures. Figures may be overlaid to show how results are sensitive to our choice of π . Even though we will obtain the entire posterior distribution of our parameters, we will also calculate 95% credible intervals, which is an alternative way of presenting effect sizes corresponding to hypotheses H(1.1) – H(3.4). Credible intervals will also be used to conduct hypothesis testing (details on hypothesis testing are below). Below are the model outcomes that will be used to test each hypothesis:

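### Bayes factors with no stated prior width decide whether the primary Aim 1 contrasts are tested overall or only in subgroups, and no overall contrast remains once a split is selected

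*Combined protocol and SAP*

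**What the plan says.** Aims & Hypotheses makes Aim 1 primary and Aims 2 and 3 secondary. Statistical analyses defines the primary comparisons as average within-person differences by condition on four outcomes.

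The same section sets the model choice: "Bayes factors will be used to determine if the effect of the condition depends on NAS-smoking status or gender". They also decide whether natural and organic share one effect. The order is explicit: "Using Bayes factors to first choose the best representation for the effects of the condition in the model" precedes model averaging, and this is repeated by outcome "so that we have one model for each of the four outcomes".

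On priors for the main analyses, "we will use uninformative priors for all model parameters". The fallback applies if there is a convergence issue "or if model fit is a concern, we will instead consider weakly informative priors". No scale, prior model odds or Bayes-factor cut-off is stated. Sensitivity to the prior is planned for carryover only.

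Hypothesis testing makes the Aim 1 tests depend on the selected structure. With no moderation there are 8 overall intervals. With moderation by NAS status or by gender there are 16, all within subgroups. With both there are 32, in four NAS-by-gender cells, and the plan marks this branch as the one it hypothesizes. No split branch lists a contrast averaged over subgroups.

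**The concern.** **(a) The selector is not defined.** A moderation term appears in one candidate model and not in another. With an improper prior on it, the Bayes factor is undefined, because the prior's arbitrary constant does not cancel. With a proper but very wide prior it is defined, but it leans towards no moderation, and the more so the wider the prior. So following the stated prior rule gives either no answer or one that turns on an unstated number.

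**(b) The declared comparison disappears.** If a split is selected for an outcome, its Aim 1 hypothesis is answered only by subgroup. There is then no single result for the study population, although the primary comparison was declared as an average.

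At stake is the form of the primary test. Each outcome may end with 1, 2, 4 or 8 intervals: one or two contrasts, times one, two or four subgroups. The four primary outcomes need not end in the same form.

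**Working it through.** **Inputs from Sample size calculations.** Mean difference 120 ml and SD 165 ml; pessimistic case with the effect halved and the covariance 50% larger; 120 subjects for Aim 1 at 90% power; 5% significance; 228 completers. The intraclass correlation of 0.5 is stated there for the gender interaction and is assumed here for puff volume. Prior widths, equal prior model odds and a cut at 1 are my assumptions, because the plan gives none.

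**1. The plan's Aim 1 figure.** SD = 165 × √1.5 = 202.1 ml. SD of a paired difference = 202.1 × √(2 × 0.5) = 202.1 ml. Effect = 60 ml.

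n = (202.1 × (1.960 + 1.282) / 60)² = 119.2, so 120. With the noncentral t, power at 120 is 89.7%. The plan's figure is therefore consistent with one two-sided contrast in an undivided sample.

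**2. Interval counts.** 4 × 2 = 8; 4 × 2 × 2 = 16; 4 × 2 × 4 = 32, all as stated. Only the first set is overall.

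**3. Precision of one moderation term.** For two groups of 114, SE = 202.1 × √(2/114) = 26.8 ml. An effect with 90% power has z = 1.960 + 1.282 = 3.24, or 86.8 ml. A 60 ml interaction has z = 60/26.8 = 2.24.

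**4. Bayes factor for no moderation, one term.** With a normal prior of mean 0 and k = prior SD / SE:

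BF01 = √(1 + k²) × exp(−(z²/2) × k²/(1 + k²)).

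A split is selected (BF01 < 1) when |z| > √(ln(1 + k²) × (1 + k²)/k²). The last two columns are the chance that a normal estimate with true z of 2.24 or 3.24 passes that limit.

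| Prior SD | k | BF01 at z = 3.24 | BF01 at z = 2.0 | Limit for the z-statistic | Selected, true 60 ml | Selected, 90%-power effect |
|---|---|---|---|---|---|---|
| 0.5 outcome SD (101 ml) | 3.78 | 0.029 | 0.60 | 1.71 | 70% | 94% |
| 1 outcome SD (202 ml) | 7.55 | 0.044 | 1.07 | 2.03 | 58% | 89% |
| 2 outcome SDs (404 ml) | 15.1 | 0.081 | 2.07 | 2.34 | 46% | 82% |
| 1,000 ml | 37.4 | 0.20 | 5.07 | 2.69 | 33% | 71% |
| 10,000 ml | 374 | 1.95 | 50.6 | 3.44 | 12% | 42% |

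At z = 3.24 the decision reverses at k = 191, near 5,100 ml (25 outcome SDs). At z = 2.0 it already changes between 0.5 and 1 outcome SD.

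**5. Two terms (natural and organic separate).** Take both estimates at 86.8 ml, with correlation 0.5 because they share the conventional condition, covariance V, and independent priors with SD τ. BF01 is the bivariate normal density of the estimates with covariance V divided by that with covariance V + τ²I. It is 1.5 at 1,000 ml and 146 at 10,000 ml, and it crosses 1 near 820 ml (4 outcome SDs).

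**6. Aim 1 power, by sample used.** For 60 ml with SD 202 ml (noncentral t, no multilevel pooling), power is 99% over 228 and 88% in a half of 114.

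The other three outcomes have no planning inputs, so no such figures can be given for them.

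**The case against.** **Uninformative priors reproduce the frequentist analysis.** The SAP says that "results using a single candidate model with a Bayesian model averaging approach are equivalent to non-Bayesian, frequentist analyses", and the sample-size section leans on this: "which makes our analyses comparable to the non-Bayesian approach that is used for sample size calculations". The first statement is limited to a single candidate model. It does not reach the choice between models, which is where the prior width matters.

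**A cut-off is implied.** Choosing the best representation suggests taking the best-supported model, a cut at 1. That is a natural reading and the one used above, but the plan does not state it, and it does not supply the prior width.

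**The branches are prespecified, and subgroup effects are the right report when moderation is present.** This stands in part. Every branch and its interval count is written down, and an overall contrast could be derived from the posterior. Average within-person differences could also be read as averages within a subgroup. But the plan does not say that an overall contrast will be tested after a split.

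**The multilevel approach to multiplicity could supply a prior or a common mean.** Possibly, but the plan links it neither to the Bayes factors nor to a named overall contrast.

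**The two gaps offset each other.** True: wide priors favour the unmoderated model, which keeps the overall contrast. They do so by working against detection of the moderation that Aims 2 and 3 are about.

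**Stronger readings to avoid.**
- A reader might infer that the primary test will be run in cells of about 57 with far less power than planned. Such a power figure assumes the same effect in every cell, and under that assumption the four-cell branch is almost never selected. How often that branch would be selected also depends on whether the model has a three-way NAS-by-gender-by-condition term, which the plan does not settle.
- A reader might infer that any moderate prior scale settles gap (a). The z = 2.0 column shows otherwise.
- A reader might infer that Aims 2 and 3 go untested if no moderation is selected. Hypothesis testing lists their subgroup effects without that condition. What is open is how this fits with keeping one model per outcome.

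**Conclusion.** Both gaps are in the text. Gap (b) needs no assumption about priors: every split branch, including the one the plan hypothesizes, drops the declared average comparison. A split is a realistic outcome. The study is sized for the gender interaction, and for NAS status "we anticipate that group means will be more extreme in the NAS/non-NAS group". At the 90%-power effect, moderate prior scales select the split 82% to 94% of the time.

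For gap (a), the unstated width moves the chance of selecting a true 60 ml interaction from 70% to 12% across the range examined. For a borderline result it changes the decision even between 0.5 and 2 outcome SDs. For a strong single-term result, only a very wide prior reverses it.

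The harm is an undefined or width-dependent choice of primary test and the loss of a study-level answer. It is not mainly loss of power: a one-way split still has 88% power per half, close to the planned 90%, on doubly pessimistic inputs. The figures rest on puff volume, intraclass correlation 0.5, equal groups, normal priors, equal prior model odds and a cut at 1. This should be fixed before the data are analysed.

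**What to change.** 1. In every branch, test H1.1 to H1.4 by natural minus conventional and organic minus conventional (or the combined contrast if one effect is selected), averaged over the NAS-by-gender cells with prespecified weights. Equal weights would match the recruitment targets. State whether the binary expectancy outcome is averaged on the probability or the log-odds scale. Report subgroup intervals as secondary.
2. For the Bayes factors on the condition-effect structure, state proper priors scaled to the outcome SD (log-odds scale for the binary outcome), the prior model odds and the cut-off. Say how these priors relate to the multilevel multiplicity approach. Repeat at half and double the scale and report whether the selected structure changes.
3. State that the Aim 2 and 3 subgroup effects are estimated from the moderated model whichever structure is selected, and reconcile this with the one-model-per-outcome wording.

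The cost is SAP wording and a few more model runs on the same data. A prior scale will have to be defended. The averaged contrast will describe the recruited half-NAS mix, not the market, where the Introduction puts NAS at roughly 3-4%.

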The study will examine the associations between condition (“organic,” “natural,” or “conventional”) and four classes of primary outcomes: 1) expectancies (binary outcome); 2) subjective ratings (continuous outcome); 3) topography (continuous outcome); and 4) immediate biomarkers of exposure (continuous outcome). Within these classes of outcomes, our primary comparisons are average within-person differences by condition in: 1) belief that the cigarette has fewer chemicals; 2) chemical aftertaste; 3) total puff volume; and, 4) salivary aldehydes concentration. We will treat analyses of all other outcomes as exploratory.

In a crossover design, where each subject experiences all conditions (such as this design), a differential carryover effect may bias the estimated effect of the condition.⁴⁵ A differential carryover effect would mean that the effect of the condition depends on the period (visit number), which is a carryover effect, and that this carryover effect is larger for certain sequences of visits or types of subjects (e.g. NAS-smoking type or gender). The traditional approach of Grizzle (1965)⁴⁶ uses only independent data if there is evidence of a carryover effect, which would mean using only data from visits 1-3 (out of 5) for all subjects in this study; on other hand, if there is no evidence of a carryover effect, then all data can be used. With a counterbalanced design, using only data from visits 1-3 would allow us to test hypotheses H(1.1)-H(3.4), but hypothesis testing would have lower statistical power compared to using data from all 5 visits. Even though counterbalancing reduces carryover effects, it is not guaranteed to prevent them. Differences in carryover effects can be incorporated within a Bayesian framework without resorting to the 'all-or-nothing' approach that follows a preliminary test⁴⁷; we will therefore use a Bayesian approach for these analyses.

In particular, a Bayesian linear and logistic mixed effects model will be used to test hypotheses H(1.1) - H(3.4). Since we do not anticipate a carryover effect, main analyses will use a prior distribution that assumes there is no carryover effect. However, sensitivity to this choice of prior will be assessed by repeating analyses under different choices of prior that allow for a carryover effect using an approach similar to Grieve (1985).⁴⁸ For example, one particular choice for this prior assumes a carryover effect is absolutely certain (more details of this prior are below).

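### Carryover is described only as a condition effect that varies by period, with no term for the previous session's descriptor, so the planned sensitivity analysis is a weak check on the no-carryover primary model

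*Combined protocol and SAP*

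**What the plan says.** Carryover is introduced in the second paragraph of Statistical analyses: "A differential carryover effect would mean that the effect of the condition depends on the period (visit number), which is a carryover effect". The same sentence adds that "this carryover effect is larger for certain sequences of visits or types of subjects". The section then sets out the traditional remedy, "which would mean using only data from visits 1-3 (out of 5) for all subjects in this study", and declines it in favour of a Bayesian treatment "without resorting to the 'all-or-nothing' approach that follows a preliminary test".

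The primary position is that "main analyses will use a prior distribution that assumes there is no carryover effect". Sensitivity is examined later in the section, where the definition returns: "if there are carryover effects, then the effect of the condition also depends on the period". For the model with carryover (M1) the plan states: "we will first use a Normal distribution with mean 0 and variance" σ_co². The analysis is then repeated over a range of prior weights between the no-carryover model M0 and M1.

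Three things are not stated: a parameter for the descriptor seen at the preceding session, which contrast will be read from M1, and which orders of the three descriptors are used. The Study overview says only that conditions are randomized and counterbalanced.

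**The concern.** The cited methods come from the two-period crossover, where a carryover difference and a condition-by-period interaction cannot be told apart. Here every participant has three descriptor sessions after the own brand session, so they can be. Carryover in this trial would mean, for example, that the conventional cigarette is judged differently because the session before it showed organic. A condition-by-period model does not use that information. Within a session it averages over the possible predecessors and leaves their difference in the residual.

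Such carryover is plausible. The same cigarette is presented as varieties of one brand, sessions may be one day apart, and a descriptor once seen cannot be washed out. The plan itself accepts that counterbalancing may not prevent carryover. The sensitivity analysis is the stated test of an assumption behind all four primary hypotheses. If it follows the definition given, it may agree with the primary result because it shares the same bias.

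**Working it through.** **Inputs.** From Sample size calculations: intraclass correlation ρ = 0.5, 228 completers, a mean difference of 120 ml with SD 165 ml, and a pessimistic case with half the effect and 1.5 times the variance. From Study procedures: own brand at Session 2, descriptors at Sessions 3-5. Assumed: all six descriptor orders used equally, a random participant intercept, and carryover reaching only the next session.

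**The plan's own figure.** n = (1.960 + 1.282)² × 1.5 × 165² / 60² = 119.2, so 120, as the plan states. With ρ = 0.5 the SD of a within-person difference equals the single-session SD, so 165 ml can serve for both.

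**Bias.** Let the response fall by d when the previous session showed natural or organic, and by 0 after conventional or own brand.
- Conventional at Sessions 4-5 always follows natural or organic, so it is shifted by -d. Organic at Sessions 4-5 follows natural half the time and conventional half the time, so its mean shift is -d/2. At Session 3 neither is shifted.
- Bias of organic minus conventional is therefore 0 at Session 3, d/2 at Session 4 and d/2 at Session 5.
- The no-carryover model gives (0 + d/2 + d/2)/3 = d/3. The condition-by-period model averaged over periods gives the same d/3. Only its Session 3 contrast is free of this bias. Natural minus conventional behaves in the same way.

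For d = 0.3 SD the bias is 0.1 SD, or 16.5 ml if the SD is 165 ml.

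**Detection.** Generalised least squares, natural and organic both carrying over by 0.3 SD, 228 participants, 5% level:

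| Test | df | Noncentrality | Power, ρ = 0.5 | Power, ρ = 0.3 to 0.7 |
|---|---|---|---|---|
| Condition by period | 4 | 1.98 | 17% | 11-32% |
| Previous descriptor | 2 | 12.92 | 91% | 80-99% |

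Frequentist power stands in here for how much the data can move the weight between M0 and M1.

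**Precision.** The no-carryover variance of a contrast is 2σ²(1 - ρ)/N = 165²/228 = 119.4, SE 10.9 ml.

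| Analysis | Variance ratio | SE, SD 165 ml | Carryover bias |
|---|---|---|---|
| No carryover | 1.00 | 10.9 ml | d/3 |
| Condition by period, averaged | 1.00 | 10.9 ml | d/3 |
| Condition by period, at Session 3, flat prior | 4.2 | 22.4 ml | 0 |
| Previous descriptor, flat prior | 1.24 | 12.1 ml | 0 |

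For ρ from 0.3 to 0.7 the ratios are 3.8-4.6 at Session 3 and 1.23-1.24 for the previous-descriptor term. In the plan's pessimistic case (60 ml, variance × 1.5) the previous-descriptor model has SE 14.9 ml and 98% power at 228, against 13.4 ml and 99% with no carryover term.

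**Sequences.** With a single three-sequence Latin square at ρ = 0.5, the previous-descriptor model itself has a variance ratio of about 4.2.

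**The case against.** The best defence is that the text is incomplete rather than wrong. M1 is never written out, its carryover effects are not listed, and the earlier paragraph does mention sequences of visits. The sentence tying carryover to period is also true as a consequence: first-order carryover makes the condition effect at Session 3 differ from that at Sessions 4-5. Counterbalancing gives some protection, nothing in the documents fixes the size of d, and this is a sensitivity analysis. All of that stands. But period dependence is the only form the plan gives to carryover, and the remark on sequences supplies no parameter. An analyst following the text would have no reason to code the preceding descriptor.

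A reader might go further and infer that the plan throws away most of the crossover's precision. The documents do not support that. The primary analysis uses all sessions, and restriction to the early visits is described in order to be declined. The 4.2 ratio applies only if the Session 3 contrast is read under a flat prior, and the plan does not say it will be. The planned Normal prior softens it: efficiency relative to no carryover is 0.46 for a prior SD of 0.2 SD and 0.70 for 0.1 SD, though shrinking the interaction also pulls the estimate back toward the biased one. Nor would the intervals be unreadable. An SE of 22.4 ml gives a 95% half-width of about 44 ml (1.96 × 22.4), against a planning effect of 120 ml.

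The two harms are also alternatives. The averaged contrast keeps the bias at no cost in precision, and the Session 3 contrast removes the bias at a cost.

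**Conclusion.** The concern holds as a fault in how the sensitivity analysis is specified. Following the stated definition gives either a contrast with the same d/3 bias as the primary model, or one free of bias from earlier descriptors at up to 4.2 times the variance. The plan does not say which. The associated test would usually miss a carryover of 0.3 SD (about 17% power, against 91%).

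These figures assume six balanced orders, a random intercept, carryover from one session to the next only, and a continuous outcome. The expectancy outcome is binary, and its figures would differ. The 0.3 SD is illustrative. The calculations do not show that carryover exists or that the primary estimates are biased.

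A separate estimate from Session 3 data alone might look like a natural safeguard, but it is not needed. Its variance ratio is 6.0 (SE 26.8 ml), and it comes close to the restricted analysis the plan declines.

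**What to change.** In both carryover paragraphs of Statistical analyses, define the carryover effects in M1 as first-order effects of the descriptor shown at the previous session (natural, organic or conventional), with none at Session 3, which follows own brand. Keep the period effects and apply the Normal(0, σ_co²) prior to these carryover effects. State that the organic minus conventional and natural minus conventional contrasts from this model are the ones reported, and that all six descriptor orders are used equally.

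The cost is SAP wording and one variable derived from session order. Participants and the primary model are unaffected. The variance in the sensitivity analysis rises by a factor of about 1.24, a loss of about 19% of the information. If only a three-sequence Latin square was used, the factor is about 4.2 and the SAP should say so.

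### The carryover sensitivity analysis labels a probability as prior odds, and its carryover variance prior has no family, scale or bound; the primary result is protected

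*Combined protocol and SAP*

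**What the plan says.** All of this is in the Statistical analyses section of the combined protocol and SAP.

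- The main analyses assume no carryover. The plan says this in words, independently of any value of π. It also names a sensitivity case in which carryover is taken as certain.
- The model weight is introduced with "we will let π be the prior odds of M_0 to M_1". M0 is the model without carryover and M1 the model with it.
- Values follow at once: "The primary analyses assume there is no carryover effect, which corresponds to π equal to 1". The sensitivity analyses take 0 ≤ π < 1.
- The purpose is to "assess the impact of a range of prior belief in a carryover effect by repeating analyses" at different values of π. On display: "Figures may be overlaid to show how results are sensitive to our choice of" π.
- Under M1 a Normal distribution with mean 0 and variance σ_co² serves "as the prior for the carryover effects, and use an uninformative prior for" σ_co², with support from 0 to ∞. No family, scale or bound is given.
- A fallback exists, but its triggers are a convergence problem or poor fit: "if model fit is a concern, we will instead consider weakly informative priors".
- On the meaning of M1: "if there are carryover effects, then the effect of the condition also depends on the period".

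**The concern.** There are two separate defects.

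**The meaning of π.** Even odds between two models are not certainty in one of them. The plan prefers a Bayesian treatment because it avoids the all-or-nothing choice that follows a preliminary carryover test. Values of π strictly between 0 and 1 are what deliver that advantage, and those are the values the mix-up distorts. The sponsor does not expect carryover, so the most relevant priors are those with P(M0) above one half. Coded as odds no greater than 1, the grid never reaches them, and figures labelled by π would show something other than their label.

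**The carryover variance prior.** σ_co² exists only in M1. Weighting M0 against M1 needs their Bayes factor, and a vague prior on a parameter found in only one model drives that factor. An improper prior leaves it undefined, and a diffuse proper prior can make it depend strongly on a scale the plan does not state. At π = 0 no Bayes factor is needed, but the answer comes wholly from M1 and so still rests on this prior. Two analysts following the same text could report different carryover checks from the same data.

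**Working it through.** **1. The plan's own value, π = 1.** If π is the odds of M0 to M1, then P(M0) = π/(1+π) = 1/2 = 0.50. Reversing the odds gives 1/(1+π) = 0.50 as well. Only P(M0) = π gives 1 at π = 1, and it also gives 0 at π = 0, which is the carryover-certain case. The stated value is therefore not reproduced under the written definition, and the values point to a probability. If odds were kept, no carryover would need π = ∞, and P(M0) = 0.9 would need odds of 9, outside the stated range.

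**2. Interior values.** Let B be the Bayes factor for M0 against M1. The documents give no value for it.

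- π as probability: posterior P(M0) = πB/(πB + 1 − π).
- π as odds: posterior P(M0) = πB/(1 + πB).
- Writing q = 1 − π, the gap (first minus second) peaks at πB = √q, where it equals (1 − √q)/(1 + √q). It tends to 0 as B goes to 0 or to infinity.
- Example at π = 0.75: √q = 0.5 and B = 0.5/0.75 = 0.67. The gap is 0.5/0.75 − 0.5/1.5 = 0.33.

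| π | Prior P(M0) if coded as odds | Largest gap, any B | Gap for B from 1/3 to 10 (assumed) |
|---|---|---|---|
| 0.25 | 0.25/1.25 = 0.20 | 0.07 | 0.02–0.07 |
| 0.50 | 0.50/1.50 = 0.33 | 0.17 | 0.08–0.17 |
| 0.75 | 0.75/1.75 = 0.43 | 0.33 | 0.09–0.33 |
| 0.90 | 0.90/1.90 = 0.47 | 0.52 | 0.09–0.52 |

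The gap is never negative, so coding as odds always gives M0 less weight than the label says. At π = 0 both codings give P(M0) = 0.

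**3. Variance prior, 0 < π < 1.** This is an illustration and everything in it is assumed: one carryover contrast estimated at z standard errors (SE), and a half-normal prior on σ_co with scale k SE. Then B = N(z; 0, 1) / ∫ N(z; 0, √(1+s²)) p(s) ds, where the second argument is the mean and the third the standard deviation. The last column uses π = 0.5 as a probability, so it equals B/(1+B).

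| z | k | B | Posterior P(M0) |
|---|---|---|---|
| 1 | 1 | 1.09 | 0.52 |
| 1 | 10 | 2.88 | 0.74 |
| 1 | 100 | 15.42 | 0.94 |
| 2 | 1 | 0.63 | 0.39 |
| 2 | 10 | 0.88 | 0.47 |
| 2 | 100 | 4.04 | 0.80 |

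At z = 2 the same data move from favouring carryover to favouring none on prior scale alone.

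A second illustration uses a toy three-period crossover with six balanced sequences. It takes 228 completers, SD 165 ml and intraclass correlation 0.5 from Sample size calculations, and assumes carryover of −40 ml after conventional and +20 ml after each of the other two. With a uniform prior on σ_co² up to 10⁴, 10⁶ or 10⁸ ml², B is 0.0036, 0.097 and 5.5.

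**4. Variance prior, π = 0.** In the same toy model, adopting M1 shifts natural minus conventional by 18.9, 19.7 and 19.8 ml under those three uniform priors, but by 9.3 ml under an inverse-gamma(1,1) prior. Only two carryover contrasts are identifiable there. A flat unbounded prior on σ_co² then gives an improper posterior (it diverges at infinity), and so does a prior proportional to 1/σ_co² (it diverges at 0).

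**The case against.** The strongest reply to the first defect is that it is a slip of one word. Both endpoints are fixed in words, the values show what was meant, and an analyst would have to ignore the next sentence to code π as odds. Miscoding would also err towards a harsher carryover check. For a given M1 prior, each intermediate posterior is a mixture of the M0 and M1 posteriors. For a quantity defined in both models, its mean and equal-tailed limits therefore stay between the two endpoint results. The overlaid figures are optional. All of this stands, and it makes the first defect the smaller one. It does not make the written definition usable.

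A reader might infer that the primary analysis becomes a 50:50 average of M0 and M1. The documents do not support that: the no-carryover assumption is stated in words and does not depend on π.

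On the second defect, it can be said that the prior is partly specified (Normal effects, support 0 to ∞) and that the plan follows a process similar to a cited Bayesian crossover paper. The first is right, and to call the prior wholly unspecified would overstate the point. What is missing is family, scale and bound. Similarity to a source does not by itself supply these, and what that source says cannot be judged from these documents. The weakly informative fallback is triggered by convergence or fit, and a Bayes factor can depend on prior scale when both are satisfactory.

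It is also fair that the illustrations do not reproduce the planned model, which has several carryover effects sharing one variance. They show how the dependence arises, not its size in this trial.

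**Conclusion.** Both defects hold, with different scope.

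- **Odds or probability.** The label at π = 1 is wrong but harmless to the primary result. Runs at 0 < π < 1 are mislabelled if coded as written, and π = 0 is unaffected. The prior probabilities and the maximum gaps of 0.07, 0.17, 0.33 and 0.52 are exact. The gap that would actually occur depends on B, which is unknown.
- **Variance prior.** All of 0 ≤ π < 1 is affected. It is tempting to treat π = 0 as safe because it needs no Bayes factor, but M1 alone rests wholly on this prior. Whether the posterior there would be improper depends on which prior is chosen and how many carryover contrasts the data identify, so that is a possibility and not a finding.

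The carryover robustness check cannot be reproduced or interpreted as written and should be corrected before analysis. No shift in the trial's own effect estimates can be derived from the documents.

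**What to change.** - Define π as the prior probability of M0, so that the prior odds are π/(1 − π). State that π = 1 is M0 alone (primary) and π = 0 is M1 alone.
- List the sensitivity values of π in advance, including some above 0.5.
- Name a proper prior for the carryover standard deviation. Scale it to the outcome SD for continuous outcomes and set it on the logit scale for the expectancy outcome and any outcome later dichotomised.
- State that the M0 posterior receives weight πB/(πB + 1 − π), and say which M1 condition effect is averaged with the single M0 effect, since under M1 that effect varies by period.
- Repeat at one wider and one narrower scale. Report every result with 0 ≤ π < 1, including π = 0, at each scale beside the π = 1 result.

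**Cost.** Some added SAP wording, one named prior per outcome type, and no new data. Changing π only re-weights existing fits, but changing the scale means refitting M1. The plan notes that "there are 2^k possible models when there are k covariates". With the six named covariates (five for topography) and one chosen form of the condition effect, that is 3 × 2⁶ + 2⁵ = 224 M1 models per scale, or 448 for two extra scales. The count grows if further covariates are added, as the plan allows. One fixed covariate set per outcome reduces it to 4 × 2 = 8 refits, or 5 × 2 = 10 if the two aldehydes are modelled separately. The drawback is that intermediate results may visibly depend on the prior scale, which is why all three scales should be shown.
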